2.2.2 Secondary

We will use the results from the biopsy as the reference standard. The significance level of Generalized linear mixed logistic or GEE logistic modeling as well as the Mann-Whitney or Student's t-test will be 0.05.

3 Study Design

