4.1 Eligibility Criteria

4.1.1 Inclusion Criteria

Individuals must meet all of the following inclusion criteria in order to be eligible to participate in the study:

1. Provide signed and dated informed consent form
2. Be conscious, willing and able to comply with all study procedures and be available for the duration of the study
3. Female, at least 21 years old
4. Be scheduled for a breast biopsy (BIRAD 4, 4A, 4B, 4C or 5)
5. Patient with an at least 1 cm mass located at <3cm depth, approachable by 2.5 inch needle
6. Be medically stable as determined by the investigator
7. If a female of child-bearing potential, must have a negative urine pregnancy test within 24 hours prior to administration of Definity.

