11.2 Analysis Plans

Radio frequency (RF) data from 3D SHAPE will be transferred to a PC for off-line analysis. 3D RF data from SHAPE will be composed of multiple 3D volumes (5 to 21 volumes) over time. Each 3D volume will consist of multiple 2D data sets (about 79 slices), which will be collected in the elevational direction. All data processing will be

performed using Matlab (R2015b; Mathworks, Natick, MA). Two regions of interest (ROI) will be selected in each elevational plane for SHAPE: one within the tumor and the other in the surrounding tissues (available top and/or bottom region of tumor). The ROIs of the tumor and surrounding area will be selected as a free form on the images generated from RF data (i.e., raw data before post-processing for on-screen display). The ROIs will be selected by the sonographer or radiologist. Then, a Fast Fourier Transform will be computed for each A-line within the ROI to obtain the frequency spectrum. The maximum magnitude from the resultant frequency spectrum will be extracted from each pre- and during infusion data sets and the ratio will be calculated for each ROI. If both top and bottom regions are selected as a surrounding area ROI, then the ratios will be averaged to one value. Finally, the obtained subharmonic signal ratios from the tumor and the surrounding area will be compared to the direct IFP measurements. Pearson's correlation coefficients will be computed between SHAPE results and direct IFP measurements by Stryker compartment pressure monitoring system. These data will also be rigorously analyzed for agreement using Bland-Altman analysis (Bland & Altman, 1999) among tumor and healthy tissue samples. To explore if the relationship between SHAPE results and IFP is confounded by or might depend on study variables collected (e.g.'s, patient characteristics, tissue/tumor characteristics, etc.) linear mixed effects or generalized estimating equations modeling will be used. Generalized linear mixed logistic or GEE logistic modeling of tumor vs. non-tumor samples will be used to explore the potential for using SHAPE results as a novel functional predictor of breast tumor malignancy. Additionally, the subharmonic signal ratio from the tumor will be used to predict the malignancy of breast tumor using a biopsy result as a gold standard. The Mann-Whitney or Student's t-test will be performed depending on the distribution of the results.

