11.3 Sample Size Considerations

The aim of the study is to determine the correlation between SHAPE results and direct measurements of IFP. The aim is to get significant result ($p < 0.05$) with sufficient power (80%) to detect at least correlation coefficient of 0.5-0.6. Therefore, the required sample size for this study is 19 -29 based on the formula for calculation is based on two-tailed test [Guenther 1977]. Thus, we chose 25 patients as our sample size.

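### The malignant-versus-benign comparison makes no allowance for unequal spread, so its true level can drift from the stated 0.05 in either direction; name one test (Welch) and one scale in advance

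*Combined protocol and SAP*

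**What the plan says.** Section 11.2 (Analysis Plans) states that "the subharmonic signal ratio from the tumor will be used to predict the malignancy of breast tumor using a biopsy result" as the reference. It then gives the test: "The Mann-Whitney or Student's t-test will be performed depending on the distribution of the results". Section 2.2.2 (Secondary) fixes the level: "The significance level of Generalized linear mixed logistic or GEE logistic modeling as well as the Mann-Whitney or Student's t-test will be 0.05".

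The plan gives no normality criterion or cut-off, no analysis scale for the ratio, no unequal-variance option and no sidedness for this test. It also gives no expected malignant fraction and no SDs. Section 11.3 sets the total: "Thus, we chose 25 patients as our sample size". That number was derived for the primary correlation, not for this comparison.

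**The concern.** Student's t, as named, pools the two variances. When the smaller group is the more variable, pooling understates the standard error and the test rejects too often. When the larger group is the more variable, the test rejects too rarely. Mann-Whitney is not a safe fallback, because its level also shifts when the groups differ in spread. A look at the shape of the data would not reliably reveal the problem.

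Both conditions could arise here. Eligibility covers BI-RADS 4 to 5 (section 4.1.1), so nothing guarantees an even split. Section 1.1 cites a mean IFP of 29 mmHg in invasive ductal carcinoma, against -0.3 to 3.6 mmHg in normal tissue, benign lesions and noninvasive carcinoma. A malignant group could therefore mix high-pressure and low-pressure lesions and be more variable. That is an inference about pressure, and the documents do not report it for the SHAPE ratio.

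At stake is whether a p-value below 0.05 for the secondary objective means what section 2.2.2 says it means.

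**Working it through.** **Inputs from the documents.** N = 25, one tumor ratio per patient (11.2, 11.3); level 0.05 (2.2.2); Mann-Whitney or Student's t (11.2).

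**Assumptions.** Two-sided test. Selection rule: Shapiro-Wilk in each group at 0.05, then Student's t if both pass, otherwise exact Mann-Whitney. Malignant:benign split from 6:19 to 19:6. Ratio of malignant to benign SD of 1, 2 or 3.

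**The plan's own figures.** There is no sample-size or power figure for this test. The range of 19 to 29 in section 11.3 belongs to the primary correlation and reproduces: the exact distribution of r gives 29 for r = 0.5 and 19 for r = 0.6 (two-sided 0.05, 80% power). The nominal 0.05 also reproduces at equal spread: the two-stage rule gives 0.050-0.051 with normal data and 0.053-0.056 with log-normal data.

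**Why the level moves.** With pooling, Student's t in effect uses the variance s_p²(1/n₁ + 1/n₂), where s_p² = [(n₁-1)σ₁² + (n₂-1)σ₂²]/(n₁+n₂-2). The true variance of the difference is σ₁²/n₁ + σ₂²/n₂. Take malignant SD 2 and benign SD 1:

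- 8:17. Pooled (7×4 + 16×1)/23 = 1.913; times (1/8 + 1/17) = 0.1838 gives 0.352. True 4/8 + 1/17 = 0.559. The true SE is √(0.559/0.352) = 1.26 times the assumed one.
- 12:13. Pooled (11×4 + 12×1)/23 = 2.435; times 0.1603 gives 0.390. True 4/12 + 1/13 = 0.410. Factor 1.03.
- 17:8. Pooled (16×4 + 7×1)/23 = 3.087; times 0.1838 gives 0.567. True 4/17 + 1/8 = 0.360. Factor 0.80.

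**Simulated level, normal data, equal means** (SD ratio 2 / 3; 40,000 trials per cell for the first three rows, 8,000 for the last two):

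| Malignant:benign | Two-stage rule | Welch |
|---|---|---|
| 12:13 | 0.062 / 0.070 | 0.050 / 0.051 |
| 8:17 | 0.124 / 0.161 | 0.054 / 0.051 |
| 17:8 | 0.020 / 0.016 | 0.049 / 0.051 |
| 6:19 | 0.157 / 0.227 | 0.060 / 0.056 |
| 19:6 | 0.009 / 0.006 | 0.048 / 0.050 |

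**Which part is responsible.** At 8:17, Student's t alone gives 0.123 / 0.158, almost the same as the two-stage rule. Mann-Whitney alone gives 0.090 / 0.113. The selection step adds little.

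**Milder differences.** Student's t alone, malignant group more variable, at 12:13, 10:15 and 8:17: SD ratio 1.25 gives 0.053, 0.058, 0.071; SD ratio 1.5 gives 0.057, 0.068, 0.089.

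**Skewed data on the raw ratio, equal means, SD ratio 2 / 3.** For log-normal data (sigma 0.5) at 8:17 the two-stage rule gives 0.145 / 0.192 and Welch 0.077 / 0.081. For exponential data Welch gives 0.092 / 0.101 at 8:17 and 0.109 / 0.114 at 6:19. Equal means is not the Mann-Whitney null, so these two-stage figures are only indicative.

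**Welch on the log ratio.** For log-normal ratios with equal medians (benign log-SD 0.4; malignant 1, 2 or 3 times that), the level is 0.050 / 0.053 / 0.052 at 8:17 and 0.048 / 0.050 / 0.051 at 12:13. This is the normal case again, as it must be, and it depends on the log ratio being roughly symmetric.

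**Power cost if variances are equal** (difference of 1.2 SD, assumed), Student against Welch: 0.82 v 0.81 (12:13), 0.80 v 0.79 (10:15), 0.76 v 0.73 (8:17), 0.69 v 0.62 (6:19). At 1.25 SD: 0.847 v 0.845 (12:13), 0.800 v 0.775 (8:17), 0.721 v 0.650 (6:19).

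**The case against.** The strongest reply is that every large figure above needs an uneven split and a large SD ratio together, and the documents predict neither. That stands. Near 12:13 the excess is one to two points even at SD ratios of 2 to 3.

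Three stronger readings are tempting, and the documents do not support them.

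- A reader might infer that choosing the test after seeing the data is what inflates the error. At equal spread the two-stage rule stays at 0.050-0.056, so the choice itself is nearly harmless. It remains undefined, which is a separate and smaller fault.
- A reader might infer that the planned test is always too liberal. No malignant fraction is given, and a malignant majority cannot be excluded among women with BI-RADS 4 to 5 masses. If the larger group is the more variable, the level falls to about 0.02 or below, and the cost is lost power.
- A reader might infer that Welch guarantees 0.05. On skewed data it can reach 0.08 to 0.11, and skew is presumably the case for which the plan keeps Mann-Whitney. Section 11.2 defines a plain ratio, and nothing in the documents shows that its log is symmetric.

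It can also be said that Student's t may be a loose label that includes Welch. The text does not say so, and settling it takes one word. If taking logs happened to equalize the spreads, Student's t on the log scale would serve as well, and Welch would then cost only the power shown above.

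**Conclusion.** The point holds as a modest improvement. Neither planned test protects the stated 0.05 when spread and group size differ together. Under the assumed splits, normal data and SD ratios of 2 to 3, the level runs from about 0.006 (19:6) to 0.23 (6:19), with 0.12 to 0.16 at 8:17 and 0.06 to 0.07 at 12:13. The main cause is unequal variance. Welch stays at about 0.05 to 0.06 in the same cells, and it holds about 0.05 in both directions on a log scale if the log ratio is roughly symmetric.

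The split, SD ratio, distribution shape, selection rule and two-sidedness are all assumptions. This is a secondary comparison in a 25-patient pilot. Success is defined on the primary correlation (section 2.2.1), and neither that analysis nor its sample size is touched.

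**What to change.** In section 11.2, replace the sentence "The Mann-Whitney or Student's t-test will be performed depending on the distribution of the results" with one along these lines:

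*The log of the tumor subharmonic signal ratio will be compared between biopsy-malignant and biopsy-benign tumors by Welch's t-test (two-sided, 0.05). Mann-Whitney will be reported as a sensitivity analysis in all cases.*

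In section 2.2.2, change the matching clause ("as well as the Mann-Whitney or Student's t-test will be 0.05") to name the same test and scale. Report group sizes and SDs on the log scale, so that readers can judge symmetry and spread.

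The cost is two sentences of text, with no added patients or procedures. It is cheap but not free: if variances turn out equal, power falls by under 1 to about 3 points for splits from 12:13 to 8:17, and by about 7 points at 6:19.

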11.3 Sample Size Considerations

The aim of the study is to determine the correlation between SHAPE results and direct measurements of IFP. The aim is to get significant result ($p < 0.05$) with sufficient power (80%) to detect at least correlation coefficient of 0.5-0.6. Therefore, the required sample size for this study is 19 -29 based on the formula for calculation is based on two-tailed test [Guenther 1977]. Thus, we chose 25 patients as our sample size.

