The use of an intravenous needle and the fluids given through the needle may cause minor discomfort, bleeding under the skin (bruise), fainting, and possible infection at the site of needle insertion. These risks are minimized by having nursing staff trained in placing IV lines perform these procedures in a safe, aseptic manner. The subjects' alternative is not to participate in this study and have only their scheduled clinical procedure(s) performed.

The invasive pressure measurement procedure (with 18G needle) has low risk similar to a stereotactic breast biopsy (mostly with 14G or larger needles). The risks includes: bruising and swelling of the breast, infection of the measurement site, and soreness at the needle injection. Also, there is low risk of infection and pain and they could be minimized by strict sterile technique and local lidocaine infiltration, respectively. The subjects' alternative is not to participate in the study.

1.4.2 **Benefits**

We do not expect any direct benefit for subjects enrolled in this study. The long-term benefits of this study will be the development of a noninvasive, safe, accurate IFP estimator. Additionally, it may lead to a novel functional predictor of malignancy in breast tumors.

2 **Study Objectives**

2.1 **Objectives**

This study is designed to compare the direct measurements of IFP in the breast tumor and its surrounding tissue with the values obtained from 3D SHAPE data (i.e., CEUS data).

2.1.1 **Primary**

The primary objective of the study is to determine if the 3D SHAPE results can be used to estimate IFPs in breast tumor and its surrounding tissue.

2.1.2 **Secondary**

The secondary objective of the study is to determine if the malignancy of breast tumor can be predicted by the 3D SHAPE results.

2.2 **Endpoints/Outcome Measures**

2.2.1 **Primary**

A Pearson's correlation coefficient above 0.5 will be considered a successful outcome.

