6.3 Treatment Period

On the visit day

- Perform Baseline Ultrasound imaging.
- Administer Definity (IV infusion)
 - Determine the optimized acoustic settings for 3D SHAPE imaging
 - Perform CEUS exam and collect 3D SHAPE data

- Wait for clearance of Definity
 - Collect 3D SHAPE data
- Local anesthesia procedures will be performed using simple Lidocaine 1%, or combined with 1:100,000 Epinephrine (EPI) before the IFP measurements.
- Take a single IFP measurement each from the breast tumor and its surrounding tissue using Stryker compartment pressure monitoring system with ultrasound imaging guide

Participants will be monitored for 30 minute following the administration of Definity.

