11.3.1 Replacement Policy

The patients who consent for the study participation but do not undergo the CEUS exam or IFP measurements will be replaced. Also, unsuccessful training cases will be replaced.

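### Twenty-five patients give 75% power at a correlation of 0.5, not the stated 80%, and that power does not apply to the success rule in section 2.2.1

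*Combined protocol and SAP*

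**What the plan says.** Section 11.3 sets a two-sided significance level of 0.05 ("based on two-tailed test [Guenther 1977") and aims for a significant result "with sufficient power (80%) to detect at least correlation coefficient of 0.5-0.6". It then states that "the required sample size for this study is 19 -29" and concludes: "Thus, we chose 25 patients as our sample size". It does not say which correlation the 25 corresponds to, or what the power is at 25. The null value is not written out; zero correlation is implied by the test and the range.

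Section 2.2.1 defines the primary outcome by another criterion: "A Pearson's correlation coefficient above 0.5 will be considered a successful outcome". It mentions no p-value, confidence limit, power or error rate.

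Three other places affect the calculation. Section 11.3.1 says that patients who "do not undergo the CEUS exam or IFP measurements will be replaced", so no allowance for dropout is needed. Section 6.3 has the team "Take a single IFP measurement each from the breast tumor and its surrounding tissue", which gives two pairs per patient; section 11.2 does not say whether the two sites are pooled in the Pearson correlation. Section 1.2 describes the relationship between subharmonic signal and pressure as inverse.

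**The concern.** Two things in section 11.3 do not fit. First, the chosen number lies inside the plan's own required range, while the power claim covers the whole range of correlations, including its lower end. If 29 patients are needed at 0.5, then 25 cannot give 80% there.

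Second, the power is for a test of zero correlation, while success is judged on whether the sample coefficient exceeds 0.5. A reader of section 11.3 could take 80% as the chance that the study succeeds, and it is not. A sample coefficient between about 0.40 and 0.50 would meet the aim in section 11.3 and miss the criterion in section 2.2.1. Unless the plan says in advance how the two relate, the reading of such a result could be settled after the data are seen.

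**Working it through.** **Inputs.** Two-sided alpha 0.05, target power 80%, true correlations 0.5 to 0.6, required N 19 to 29 and chosen n = 25 (all section 11.3); success at r above 0.5 (section 2.2.1); no dropout allowance (section 11.3.1). Assumed: null correlation zero, bivariate normal data, one independent pair per patient, and r counted in the expected direction.

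**Step 1: reproduce 19 to 29.** By Fisher's z, N = ((1.960 + 0.842) / atanh(ρ))² + 3.
- ρ = 0.5: atanh = 0.5493; (2.8016 / 0.5493)² + 3 = 29.0.
- ρ = 0.6: atanh = 0.6931; (2.8016 / 0.6931)² + 3 = 19.3.

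The exact distribution of the sample correlation gives 29 (power 81.4%; 28 gives 79.9%) and 19 (power 81.4%). The plan's range is reproduced, and its upper end is the requirement at 0.5. A one-sided test would give 15 to 23, and a fixed-X regression calculation 17 to 26, so neither is what the plan used.

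**Step 2: significance threshold at n = 25.** With t(0.975, 23 df) = 2.069, critical |r| = 2.069 / √(23 + 2.069²) = 0.396.

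**Step 3: power and chance of success at n = 25 (exact distribution).** The last column is the difference of the two before it.

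| True correlation | Power to reject zero | Chance that r exceeds 0.5 | Significant, but r not above 0.5 |
|---|---|---|---|
| 0.50 | 74.9% | 52.1% | 22.8% |
| 0.55 | 84.2% | 65.0% | 19.2% |
| 0.60 | 91.3% | 77.2% | 14.1% |

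Power reaches 80% at a true correlation of 0.526. The chance of meeting the success rule reaches 80% at 0.613, above the whole range named in section 11.3. As a check by Fisher's z at ρ = 0.5: 0.5493 × √22 − 1.960 = 0.617, which gives 73.1%, close to the exact 74.9%.

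**Step 4: what single results look like at n = 25.** A sample r of 0.45 has two-sided p = 0.024: significant, but not a success. A sample r of 0.5 has p = 0.011 and a Fisher 95% CI of tanh(0.5493 ± 1.960/√22) = 0.13 to 0.75.

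**Step 5: sensitivity to the unit of analysis.** If both sites in every patient were pooled and treated as 50 independent pairs, power at 0.5 would be 96.7%. This is an upper bound, because it ignores the correlation between two sites in one patient. The chance that r exceeds 0.5 at a true 0.5 would still be 51.4%.

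**The case against.** The strongest reply on power is that section 11.3 names a range of correlations and a matching range of N, and picks a number from inside it. At 25 patients, 80% is reached at 0.526, within the stated range, and power at 0.6 is 91%. That much stands: the shortfall is confined to true correlations from 0.50 to about 0.53 and is 5 points at most. But the claim is worded as covering at least 0.5, and the plan's own upper N is the 0.5 requirement, so the lower end belongs to the claim.

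On the success rule, a reader might infer that 25 patients are the reason for the 52%, or that the stated 80% is a wrong figure for section 2.2.1. The documents support neither. A point-estimate threshold placed at the true value is met about half the time at any sample size (51.9% at n = 29), and no power is stated for that rule.

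A reader might also infer that the plan issues opposite verdicts on the same result. It does not: only section 2.2.1 defines success, and section 11.3 states the aim used for sizing. A result can be significant and still too weak to count as a success. What is missing is a sentence saying so.

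It is also tempting to make p < 0.05 the success rule. That would lower the bar from 0.5 to about 0.40, where the 95% CI runs from about 0.00 to 0.68. For an objective of estimating pressure, a minimum size of correlation is a defensible requirement, and nothing in the documents calls for removing it.

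Finally, the study is a pilot with invasive measurements, which argues against enlarging it and against treating a 5-point shortfall as critical.

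**Conclusion.** The point holds at moderate severity. As written, the 80% in section 11.3 is not met at the lower end of its own range: 25 patients give 75% at 0.5 and reach 80% at about 0.53. The power belongs to the test of zero correlation and says nothing about the rule in section 2.2.1, whose chance of being met is 52% to 77% for true correlations of 0.5 to 0.6.

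The power figures rest on one independent pair per patient, which fits a sample size counted in patients but is not stated. Pooling the two sites would change them. The 52% at a true 0.5 hardly depends on this. The success-rule figures also read the 0.5 threshold as a magnitude in the expected direction; the documents do not say this, and section 1.2 suggests that the raw coefficient may be negative. The shortfall is no reason to change the sample size.

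**What to change.** Keep 25 patients and the 0.5 success threshold.

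- In section 11.3, replace the power statement with: 25 patients, one pair per patient, give 80% power (two-sided 5%) to reject zero correlation when the true correlation is about 0.53 or more in absolute value, and 75% at 0.5.
- Add that this power does not apply to the rule in section 2.2.1, and give that rule's chance of being met: 52% to 77% for true correlations of 0.5 to 0.6, in the expected direction.
- State that section 2.2.1 alone decides success, so a significant coefficient between 0.40 and 0.50 is evidence of correlation but not a success. Report the coefficient with its 95% CI in every case.

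The cost is wording only: no added patients, procedures or analyses beyond the interval. The one drawback is that the stated power looks slightly less favourable.

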11.3.1 Replacement Policy

The patients who consent for the study participation but do not undergo the CEUS exam or IFP measurements will be replaced. Also, unsuccessful training cases will be replaced.

11.3.2 Accrual Estimates

At the Jefferson-Honickman Breast Imaging Center, a breast biopsy is performed on more than 500 women each year. We expect that 25 subjects can be enrolled within 15 months.

12 Source Documents and Access to Source Data/Documents

Study staff will maintain appropriate medical and research records for this study, in compliance with ICH E6, and regulatory and institutional requirements for the protection of confidentiality of participant information. Study staff will permit authorized representatives of SKCC and regulatory agencies to examine (and when required by applicable law, to copy) research records for the purposes of quality assurance reviews, audits, and evaluation of the study safety, progress and data validity.

13 Quality Control and Quality Assurance

3D SHAPE data including ultrasound imaging and CRFs will be subject to a strict QA review by the study coordinator and PI at TJU. Results of the QA review will be shared on the quarterly basis with additional training provided, if necessary.

14 Ethics/Protection of Human Participants

